6.6.5.2. Other Laboratory Parameters

All other parameters collected on the eCRF will be listed in dedicated listings presenting all corresponding collected information on the eCRF.

- Coagulation: activated partial thromboplastin time (aPTT) and prothrombin time (INR);
- Urinalysis: all urinalysis parameters;
- Other parameters: hormone (TSH, free T4, ACTH), and immunology parameters (HBV, HCV), AFP, PIVKA-II;
- Pregnancy test.

The listings of laboratory results will be provided for all laboratory parameters. The listings will be sorted by parameters and assessment dates or visits for each patient. Laboratory values that are outside the normal range will also be flagged in the data listings, along with corresponding normal ranges. A listing of CTCAE grading will also be generated for those laboratory tests.

In addition, listings of abnormal values will be provided for hematology, chemistry, urinalysis, coagulation parameters. If there is at least one abnormal assessment for any parameter, all the data for that laboratory parameter will be included into the listing.

For all tests not mentioned above but present in the clinical data, a listing of patients with at least one result for the relevant test will be provided.

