1.2.3. Axitinib (INLYTA[®], AG 013736)

One of the investigational products in the present clinical trial is axitinib (INLYTA[®], AG 013736), an oral, small molecule, TKI selective for VEGFRs 1, 2, and 3, approved multinationally for the treatment of advanced RCC after failure of one prior systemic therapy (actual indication varies according to region/country).

Axitinib is an adenosine triphosphate (ATP) competitive inhibitor that binds to the unphosphorylated (non activated) “DFG out” conformation of the catalytic domain of a receptor tyrosine kinase. In enzymatic assays, axitinib was found to be highly potent ($K_i = 28$ picomolar) against the kinase activity of juxta membrane (JM) domain containing human VEGFR 2 recombinant protein. In additional kinase assays, axitinib showed potent and ATP competitive inhibition of the VEGFRs 1, 2, and 3 and PDGFR- β , but not other closely related family kinases. Receptor binding studies and cell based assays confirmed that axitinib is a potent and selective inhibitor of VEGFRs 1, 2, and 3. Axitinib was shown to have antiangiogenic activity in a number of models including spontaneous pancreatic islet cell tumors of RIP TAG 2 transgenic mice model and demonstrated antitumor efficacy including marked cytoreductive antitumor activity in multiple tumor models implanted in athymic mice.

Overall, the adverse events reported for axitinib in clinical studies were considered generally tolerable and manageable. For single agent axitinib, the most common adverse events (>20% of patients) reported from 1445 cancer patients regardless of causality included diarrhea, hypertension, decrease appetite, nausea, weight decreased, dysphonia, palmar-plantar erythrodysesthesia syndrome, hypothyroidism, and proteinuria. Grade ≥ 3 events that occurred most frequently were hypertension, fatigue, and diarrhea.

The most common adverse events reported in patients with advanced HCC who received axitinib single agent in randomized Phase 2 study (n = 133) were diarrhea, hypertension, decreased appetite, fatigue, abdominal pain, palmar-plantar erythrodysesthesia syndrome, weight decreased, nausea, dysphonia and hypothyroidism.¹⁵ Grade 3 events that occurred most frequently were hypertension, diarrhea and palmar-plantar erythrodysesthesia syndrome. Overall safety profile in patients with advanced HCC was similar to known safety profile of axitinib single agent.

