1.2.4. Clinical Experience of Combination therapy of avelumab plus axitinib

The combination of avelumab with axitinib is being tested in study B9991002, a Phase 1b open-label, dose-finding study aiming to evaluate the safety, pharmacokinetics (PK) and

pharmacodynamics of avelumab in combination with axitinib in patients with previously untreated advanced RCC. This study also evaluated preliminary antitumor activity as secondary endpoint. This study was designed to establish the dosing regimen of avelumab and axitinib to be used for any further study with this combination. Study B9991002 is comprised of a dose-finding phase and a dose-expansion phase. The initial doses to be tested (Dose Level 1, [DL1]) were avelumab 10 mg/kg IV Q2W in combination with axitinib 5 mg orally (PO) twice a day (BID) continuously, with 2 lower dose levels to be explored only if the maximum tolerated dose (MTD) was exceeded in DL1.

The dose-finding phase was completed on 12 February 2016. The 6 patients enrolled in this phase of the study completed the 4-week DLT follow-up period as per protocol (corresponding to 2 cycles of 2 weeks each). There was 1 DLT reported: Grade 3 proteinuria, related to axitinib per investigator assessment, which resolved after reducing the dose of axitinib to 3 mg BID. As of 12 February 2016, the AEs recorded in the dose-finding phase were mostly low grade and manageable, with no new unexpected safety signals for the combination when compared to the safety profile of each drug as monotherapy. No patients discontinued the combination due to AEs. Based on these findings, the MTD/recommended Phase 2 dose (RP2D) for the combination is avelumab 10 mg/kg IV Q2W and axitinib 5 mg PO BID continuously. Enrollment in the dose-expansion began on 15 February 2016, with a target enrollment of approximately 48 patients. As of 15 August 2016, 46 patients were enrolled and started treatment in this part of the study, and 52 patients were treated overall (6 patients in the dose-finding part and 46 patients in the dose-expansion part).

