8.2.2. Abnormal Test Findings

Abnormal objective test findings should be recorded as AEs when any of the following conditions are met:

- Test result is associated with accompanying symptoms; and/or
- Test result requires additional diagnostic testing or medical/surgical intervention; and/or
- Test result leads to a change in study dosing (outside of any protocol-specified dose adjustments) or discontinuation from the study, significant additional concomitant drug treatment, or other therapy; and/or
- Test result is considered to be an AE by the investigator or sponsor.

Merely repeating an abnormal test, in the absence of any of the above conditions, does not constitute an AE. Any abnormal test result that is determined to be an error does not require recording as an AE.

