9.4.1.2. Laboratory Test Abnormalities

Laboratory test results will be graded according to the NCI CTCAE v. 4.03 severity grade. The frequency of patients with laboratory test abnormalities will be summarized according to the worst grade for each laboratory test.

For laboratory tests without an NCI CTCAE grade definition, results will be categorized as normal (within normal ranges), abnormal, or not done.

Shift tables will be provided to examine the distribution of laboratory abnormalities.

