3. ENDPOINTS AND BASELINE VARIABLES: DEFINITIONS AND CONVENTIONS

3.1. Primary Endpoints

- Adverse events (AEs) and laboratory abnormalities as graded by National Cancer Institute (NCI) Common Terminology Criteria for Adverse Events (CTCAE) v.4.03.

AEs will be graded by the investigator according to the CTCAE v.4.03 and coded using the Medical Dictionary for Regulatory Activities (MedDRA).

Laboratory abnormalities as characterized by type, severity (as graded by NCI-CTCAE v.4.03) and timing.

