6.1. Primary Endpoints

6.1.1. Adverse Events and Laboratory Abnormalities

6.1.1.1. Primary Analysis

Refer to [Sections 6.6.1, 6.6.2, 6.6.3, 6.6.4 and 6.6.5](#).

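### The SAP only lists coagulation, urine protein and thyroid results, so the laboratory part of the primary analysis has no counts or baseline shifts for them, contrary to Protocol 9.4.1.2

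*SAP*

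**What the plan says.** The SAP's primary endpoint (3.1) is "Adverse events (AEs) and laboratory abnormalities as graded by National Cancer Institute (NCI) Common Terminology Criteria for Adverse Events (CTCAE) v.4.03". SAP 6.1.1.1 defines the primary analysis only by reference to Sections "6.6.1, 6.6.2, 6.6.3, 6.6.4 and 6.6.5", so SAP 6.6.5 is its laboratory part.

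Protocol 9.4.1.2, under the analysis of primary safety endpoints, makes three commitments:

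- For graded results: "The frequency of patients with laboratory test abnormalities will be summarized according to the worst grade for each laboratory test".
- For the others: "For laboratory tests without an NCI CTCAE grade definition, results will be categorized as normal (within normal ranges), abnormal, or not done".
- Shift tables, with no test exempted.

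Protocol Table 5 lists the required tests. They include PT or INR, PTT or aPTT, urine protein by dipstick (with a 24-hour collection or protein/creatinine ratio at 2+ or more), TSH and free T4.

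SAP 6.6.5.1 gives grade and shift tables for one named list of hematology and serum chemistry tests, and normal-to-abnormal shift counts for a second named list. SAP 6.6.5.2 then says: "All other parameters collected on the eCRF will be listed in dedicated listings presenting all corresponding collected information on the eCRF". It names coagulation, all urinalysis and the hormones, including TSH and free T4, among those parameters. The listings carry out-of-range flags, normal ranges and CTCAE grades.

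**The concern.** The two documents prescribe different summaries for the same primary endpoint. Followed as written, the SAP counts patients with shifts in chloride, uric acid or total protein, but not patients with an abnormal TSH, INR or urine protein.

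The omitted tests matter in this trial. On single-agent axitinib the protocol's most common adverse events end with "palmar-plantar erythrodysesthesia syndrome, hypothyroidism, and proteinuria". For the dose-finding phase of the combination in renal cell carcinoma it reports: "There was 1 DLT reported: Grade 3 proteinuria, related to axitinib per investigator assessment". INR is a Child-Pugh component (Protocol Appendix 2), in a disease where the protocol says most patients have cirrhosis.

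Both documents let the SAP depart from the protocol, but say that major changes to the primary endpoint analysis will also appear in a protocol amendment. Protocol 9.4.1.2 still carries the wider rule.

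**Working it through.** **1. The only design figure stated.** Protocol 9.1 and SAP 5.1.1 give at least 88% probability of seeing an AE of 10% incidence in 20 patients. Exact binomial: 1 − 0.9^20 = 0.8784, which rounds to 88%. The point does not depend on this figure.

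**2. Required tests against the SAP's tables.**

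| Test in Protocol Table 5 | Graded list, SAP 6.6.5.1 | Ungraded list, SAP 6.6.5.1 | SAP 6.6.5.2 |
|---|---|---|---|
| PT/INR | no | no | listing |
| PTT/aPTT | no | no | listing |
| Urine protein | no | no | listing |
| TSH, free T4 | no | no | listing |
| Chloride, uric acid, total protein (for comparison) | no | yes | not named |

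SAP 6.6.5.1 also has a general statement that results outside CTCAE will be shown as below, within or above normal. It does not rescue the omitted tests. It stands in the hematology and chemistry section, that section then names the parameters it applies to in this study, and SAP 6.6.5.2 assigns the thyroid tests to listings by name.

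**3. What the AE tables recover.** SAP 6.6.1.1 tabulates treatment-emergent AEs by system organ class, preferred term and worst grade, and is itself part of the primary analysis. Any case recorded as an AE is counted there. Protocol 8.2.2 makes an abnormal result an AE if any one condition is met: symptoms, further testing or intervention, certain changes in dosing, discontinuation or treatment, or investigator or sponsor judgement. Taking the tests in turn:

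- *Urine protein.* The dosing condition reads "Test result leads to a change in study dosing (outside of any protocol-specified dose adjustments", so axitinib being withheld under Protocol Table 2 would not trigger it. But a dipstick of 2+ or more requires quantification, which arguably meets the further-testing condition. Most relevant cases should reach the AE tables.
- *Thyroid.* Dysfunction needing hormone treatment meets the intervention condition. It also enters the irAE tables if the other steps of SAP Appendix 1 are met. A symptom-free, untreated TSH or free T4 shift can meet no condition, and the irAE algorithm requires that treatment was given, unless medical review adds the case.
- *INR and aPTT.* A symptom-free shift that prompts no action can likewise meet no condition.

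No AE table gives a baseline-to-worst shift for any of these tests.

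**4. Whether the protocol's rates size the gap.** In the combination study (Protocol 1.2.4), proteinuria was reported in 5/47 and hypothyroidism in 7/47. If those rates carried over to 20 patients (an assumption):

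- Proteinuria: 20 × 5/47 = 2.1 expected; chance of at least one = 1 − (42/47)^20 = 0.895.
- Hypothyroidism: 20 × 7/47 = 3.0 expected; chance of at least one = 1 − (40/47)^20 = 0.960.
- At the single-agent figure of more than 20%: more than 20 × 0.20 = 4 patients for each.

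All of these are AE rates, so they count the patients whom the AE tables would capture. They show that the tests are worth summarising. They say nothing about how many abnormal results go unrecorded as AEs, and the documents give no figure for that.

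**The case against.** The strongest reply is that little is lost. The AE tables are also primary and give a rate and a worst grade for recorded cases. The listings flag abnormal values and show grades, and with 20 patients and no hypothesis test a reader could count by hand. Listing a few parameters instead of tabulating them, with the endpoint unchanged, is not clearly a major modification that needs an amendment.

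Much of this stands, and it rules out several stronger readings that a reader might infer:

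- *That the primary safety result will contain no rate or worst grade for proteinuria, hypothyroidism or INR increase.* The AE tables contradict this for every case recorded as an AE.
- *That 2, 3 or 4 of 20 patients would go uncounted.* Those are AE expectations, as shown above. The most common AEs listed from the axitinib study in advanced HCC (n = 133) include hypothyroidism but not proteinuria.
- *That INR prolongation is a toxicity the protocol expects.* The available text names it for neither drug. Its relevance rests on Child-Pugh scoring.
- *That the protocol demands a grade frequency for every test.* For ungraded tests it asks only for categories. The SAP tabulates neither form for these tests.

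What does not stand is the claim that listings are equivalent. A listing pre-specifies no count, denominator, worst value per patient or baseline shift, and the protocol asks for summaries.

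**Conclusion.** The conflict is real and follows directly from the texts. The laboratory part of the primary analysis omits counts, percentages and baseline shifts for PT/INR, aPTT, urine protein, TSH and free T4, although Protocol 9.4.1.2 excludes no required test. In practice the loss is narrower: abnormal results never recorded as AEs, clearest for symptom-free thyroid or coagulation shifts and weaker for proteinuria, plus the baseline shifts for all of them. Its size cannot be estimated from the documents. The data are collected and listed, so the gap is in pre-specification, not data collection.

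Two limits apply. Whether the departure is major enough to need a protocol amendment is a judgement. The sampling times for these tests are in the Schedule of Activities, which could not be checked here, so the yield of the shift tables is uncertain. Overall this is a minor to moderate reconciliation of protocol and SAP.

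**What to change.** In SAP 6.6.5, add PT/INR, aPTT, urine protein (dipstick, with the 24-hour or protein/creatinine value where obtained), TSH and free T4 to the on-treatment frequency tables and the baseline-to-worst shift tables. Use the CTCAE v4.03 grade where one exists, and otherwise low/normal/high, or normal/abnormal where direction does not apply. State the denominator for each test, as SAP 6.6.5.1 already does for graded tests. Keep the listings in SAP 6.6.5.2.

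This brings the SAP into line with Protocol 9.4.1.2 for these tests. The cost is a change of SAP wording and a few descriptive tables from data already on the eCRF, with no new sampling.

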6.6.6. Vital Signs

Weight for the purposes of dose calculation will be recorded at screening and within 3 days pre-dose Day 1 of each cycle. Height will be measured at screening only.

Vital sign summaries will include all vital sign assessments from the on-treatment period. The average of the replicate measurements should be determined at each time point prior to summarizing the data. All vital sign assessments will be listed, and those collected outside the on-treatment period will be flagged in the listing.

All vital sign parameters will be summarized using descriptive statistics (mean, SD, median, Q1, Q3, minimum, and maximum) of actual values and changes from baseline for each visit over time. End of Treatment visit will be summarized separately. The changes computed will be the differences from baseline.

6.6.7. Electrocardiogram

ECG summaries will include all ECG assessments from the on-treatment period. All ECG assessments will be listed, and those collected outside the on-treatment period will be flagged in the listing. QTcB and QTcF will be derived based on RR and QT (see below). The average of the replicate measurements should be determined after the derivation of the individual parameter at each time point.

Selecting Primary QT Correction for Heart Rate

The analysis of QT data is complicated by the fact that the QT interval is highly correlated with heart rate. Because of this correlation, formulas are routinely used to obtain a corrected value, denoted QTc, which is independent of heart rate. This QTc interval is intended to represent the QT interval at a standardized heart rate. Several correction formulas have been proposed in the literature. For this analysis we will use some of those methods of correction, as described below. The QT interval corrected for heart rate by the Bazett's formula, QTcB, is defined as

$$QTcB = \frac{QT}{\sqrt{RR}},$$

the QT interval corrected for heart rate by the Fridericia's formula, QTcF, is defined as

$$QTcF = \frac{QT}{\sqrt[3]{RR}},$$

where RR represents the RR interval of the ECG, in seconds, and can be estimated as 60/Heart Rate.

Although Bazett's correction is the historical standard, it does not perform well when heart rate fluctuates. Fridericia's formula may perform better under these conditions. If QTcB and QTcF methods do not adequately correct for HR and there are a sufficient number of patients (eg, >30) with baseline ECGs, an alternate correction to achieve the goal of getting uncorrelated QTc and RR is based on a linear regression methods which yields, theoretically, uncorrelated QTc and RR.

Linear regression method:

- Fit a model $QT = a + b \times RR$ to baseline data
- Use the estimated slope, \hat{b} , to correct QT
- Corrected QT for heart rate will be computed as follows:

$$QTcP = QT + \hat{b} \times (1 - RR)$$

Data will be summarized using QTcF and QTcB. However, if these are not appropriate for the data set due to an observed large correlation between corrected QT and HR using the baseline assessments, the results will also be summarized using QTcP.

ECG Summaries

The following analyses will be performed for each applicable ECG parameters (RR, PR, QRS, QT, ventricular rate -denoted as HR in what follows-, and QTc) by treatment group, during the on-treatment period. The denominator to calculate percentages for each category is the number of patients evaluable for the category.

- Pearson correlation between QT and HR, QTc (QTcB, QTcF and, if applicable, QTcP) and HR using individual (non-averaged) baseline assessments;
- For each of the ECG parameters (HR, and QT, QTc, QRS, PR intervals), descriptive statistics at baseline, at each post-baseline time point and changes from baseline at each post-baseline time point;
- Frequency (number and percentage) of patients with notable ECG values according to the following categories:
 - QT/QTc increase from baseline >30 ms, >60 ms;
 - QT/QTc >450 ms, >480 ms, >500 ms;
 - HR \leq 50 bpm and decrease from baseline \geq 20 bpm;
 - HR \geq 120 bpm and increase from baseline \geq 20 bpm;
 - PR \geq 220 ms and increase from baseline \geq 20 ms;
 - QRS \geq 120 ms.

Patients with notable ECG interval values and qualitative ECG abnormalities will be listed for each patient and time point and the corresponding notable values and abnormality findings will be included in the listings.

Unscheduled ECG measurements will not be used in computing the descriptive statistics for change from baseline at each post-baseline time point. However, they will be used in the analysis of notable ECG changes and the shift table analysis of notable QT parameters.

6.6.8. MUGA/ECHO

LVEF% will be summarized using simple descriptive statistics (mean, SD, median, Q1, Q3, minimum, and maximum) of actual values and changes from baseline for each nominal visit over time. In addition, LVEF% will be summarized as frequency (number and percentage) of patients with:

- a shift from baseline normal to at least one result below the institutional lower limit of normal during the on-treatment period;
- \geq 10-point decrease from baseline in LVEF% during the on-treatment period;

- ≥ 10 -point decrease from baseline in LVEF% to a post-baseline value $< LLN$ during the on-treatment period;
- ≥ 15 -point decrease from baseline in LVEF% during the on-treatment period;
- ≥ 15 -point decrease from baseline in LVEF% to a post-baseline value $< LLN$ during the on-treatment period.

Clinically significant findings will be listed.

6.6.9. Physical Examination

The findings of the significant change since the previous physical examination will be presented in a data listing.

6.6.10. ECOG Performance Status

The ECOG shift from baseline to highest score during the on-treatment period will be summarized by treatment group. ECOG performance status with shift from ECOG=0 or 1 to ECOG 2 or higher will also be presented in a data listing.

7. INTERIM ANALYSES

No formal interim analysis will be conducted for this study.

9. APPENDICES

Appendix 1. Immune-Related Adverse Events

The MedDRA PTs and clusters for irAEs are defined in the Safety Review Plan (SRP) for avelumab.

Immune-related AEs (irAEs) will be programmatically identified as outlined in Table 11. This case definition is hierarchical, ie, each step is only checked for patients and events that have already met the prior step.

Table 11. Case Definition for irAEs

Step	Selection Criteria	Additional Notes
1	Event selected based on a list of pre-specified MedDRA PTs within clusters. These are included in the SRP as Tier1 events (Immune-mediated xxxx). If AE matches the list then it is in for the next step	
2	AE onset during 1 st study drug administration or anytime thereafter through 90 days after last dose of study treatment	This is regardless of start of new anti-cancer drug therapy and regardless of TEAE classifications
3	Answer in the AE eCRF page to ‘Was another treatment given because of the occurrence of the event’ is ‘YES’	
4	AE treated with corticosteroids or other immunosuppressant therapy. For endocrinopathies only: AE required hormone replacement	Look in the conmed pages for AE identifiers that match the AEs from Step 3. For each of such AEs if A) OR B) OR C) below are met then the AE is in for the next step A) conmed ATC code is in (H02A, H02B, D07, A01AC, S01BA, S01BB, L04AA, L04AB, L04AC, L04AD, L04AX A07EA) and AE PT is in any of the irAE clusters. B) conmed ATC code is in (H03A, H03B) and AE PT is in one of the irAE clusters associated with “Immune-mediated endocrinopathies” C) conmed ATC code is A10A and AE PT is in the irAE cluster associated with “Immune-mediated endocrinopathies: Type I Diabetes Mellitus”

5	
A) No clear etiology (other than immune mediated etiology)
 
B) Histopathology / biopsy consistent with immune-mediated event
 
Event is in if [Answer to 5B1 and 5B2 is YES (regardless of answer to 5A)] OR [Answer to 5B1 is YES AND answer to 5B2 is NO AND answer to 5A is NO] OR [Answer to 5B1 is NO AND answer to 5A is NO]
	
A) From the AE eCRF page
 
Is the AE clearly related to an etiology other than immune-mediated etiology? Yes / No
 
If answer is Yes, check all that apply:
 
 • Underlying malignancy / progressive disease. • Other medical conditions. • Prior or concomitant medications / procedures. • Other. Specify. 
B) From the AE eCRF page
 
B1) Was there a pathology /histology evaluation performed to investigate the AE? Y/N
 
B2) If answer to the above is Yes, does the pathology/histology evaluation confirms an immune mediated mechanism for the AE? Y/N
 
B3) If pathology / histology evaluation performed to investigate the AE, provide summary of relevant findings of the pathology /histology report. (Free Text)

---	---	--

The data set associated with irAEs may be refined based on medical review. The final data set including any changes based on medical review (eg, addition of cases that are not selected by the programmatic algorithm) will be the basis of the irAE analyses.

